9.2.2 Secondary Endpoint(s)

The first secondary endpoint is PFS. PFS will be programmatically determined based on the disease progression date provided by the investigator and is defined as the time between the date of randomization and the date of first progression (local, regional or distant metastasis) or death (whatever the cause), whichever occurs first. (Note: a subject who dies without reported progression will be considered to have progressed on the date of death.) For subjects who remain alive and whose disease has not progressed, PFS will be censored on the date of last evaluable disease assessment.

The second secondary endpoint (OS) is defined as the time between the date of randomization and the date of death. For subjects without documentation of death, OS will be censored on the last

date the subject was known to be alive. OS will be followed continuously while subjects are on the study drug and every 3 months via in-person or phone contact after subjects discontinue the study drug.

To third secondary endpoint to compare the local control of irradiated tumor provided by SBRT in combination with nivolumab versus nivolumab and ipilimumab will be assessed by the local control rate of the irradiated lesion.

The fourth secondary endpoint (to assess the safety and tolerability of nivolumab, SBRT and ipilimumab) will be measured by the incidence of adverse events, serious adverse events, deaths, and laboratory abnormalities.

The fifth secondary endpoint (to evaluate PD-L1 expression as a predictive biomarker) will be measured by the endpoint RFS based on PD-L1 expression level.

The sixth secondary objective (to evaluate HRQoL) will be measured by mean changes from baseline in the EORTC-QLQ-C30 global health status/QoL composite scale and by mean changes from baseline in the remaining EORTC QLQ-C30 scales in all randomized subjects.

9.3 Analyses

9.3.1 Demographics and Baseline Characteristics

Demographic and baseline characteristics will be summarized by treatment arm as randomized using descriptive statistics for all randomized subjects.

9.3.2 Efficacy Analyses

9.3.2.1 Primary Endpoint Methods

Objective-response rate (ORR) including Complete Response (CR) rate, Partial Response (PR) rate, and Stable Disease (SD) rate will be calculated through exact binomial distribution with a 2-sided 95% confidence interval among patients who obtain a least one dose of study drug.

9.3.2.2 Secondary Endpoint Methods

The PFS analyses will be conducted using a two-sided log-rank test stratified by prior immunotherapy exposure in randomized subjects. The hazard ratio and corresponding two-sided 95% CI will be estimated using a Cox proportional hazards model, with treatment group as a single covariate, stratified by the above factors. PFS curves, PFS medians with 95% CIs, and PFS rates at 6, 12, 24 and 36 months with 95% CIs will be estimated using Kaplan-Meier methodology.

The OS analysis will be conducted using a two-sided log-rank test stratified by prior immunotherapy exposure at screening in randomized subjects. The hazard ratio and corresponding two-sided (1-adjusted α)% CI will be estimated using a Cox proportional hazards model, with treatment arm as a single covariate, stratified by the above factors. OS curves, OS medians with 95% CIs and OS rates at 12 and 24 months with 95% CIs will be estimated using Kaplan-Meier methodology.

The local control (LC) of irradiated lesions will be conducted using a two-sided log-rank test stratified by prior immunotherapy exposure at screening in randomized subjects. The hazard ratio and corresponding two-sided (1-adjusted α)% CI will be estimated using a Cox proportional hazards model, with treatment arm as a single covariate, stratified by the above factors. LC curves,

LC medians with 95% CIs and LC rates at 12 and 24 months with 95% CIs will be estimated using Kaplan-Meier methodology.

To evaluate PD-L1 expression as a predictive biomarker, a Cox proportional hazards model will be used to test the interaction between PD-L1 expression (positive vs negative) and treatment arm for the primary and secondary endpoint. Additionally, ORR will be analyzed within each PD-L1 expression subgroup (positive and negative) including log-rank tests and hazard ratios with corresponding confidence intervals. PFS curves and medians will be estimated using Kaplan-Meier methodology. These analyses will be descriptive and not adjusted for multiplicity.

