- To assess the overall safety and tolerability of nivolumab and ipilimumab versus SBRT plus nivolumab and ipilimumab in subjects with metastatic Merkel cell carcinoma.
- To evaluate whether PD-L1 expression is a predictive biomarker for ORR.
- To evaluate the Health Related Quality of Life (HRQoL) as assessed by European Organisation for Research and Treatment of Cancer (EORTC) QLQ-C30.

Exploratory: See [Section 1.3.3](#) of the protocol.

Study Design:

This is a Phase 2, randomized, multi-institutional study of nivolumab and ipilimumab alone versus in combination with SBRT for subjects (≥ 18 years) with metastatic Merkel Cell Carcinoma. Approximately 50 subjects will be randomized 1:1 and stratified by prior immunotherapy exposure. Dose reductions will not be allowed.

Treatment Arms:

Randomized 1:1 [Arm A: Arm B]: Treatment until progression on either arm.

Arm A:

Nivolumab 240 mg IV over 30 min q2 weeks and Ipilimumab 1 mg/kg IV over 30 min q6 weeks until progression or unacceptable toxicity

Arm B:

Nivolumab 240 mg IV over 30 min q2 weeks and Ipilimumab 1 mg/kg IV over 30 min q6 weeks until progression or unacceptable toxicity

Radiation to be given at the start of week 2

- 8 Gy x3 doses in over ≤ 2 weeks

SBRT should begin the week following the first dose of nivolumab and ipilimumab. All sites other than skin should receive SBRT in consecutive days. Skin lesions can be treated every other day.

The number of lesions receiving SBRT will be at the treating physician's discretion based on anticipated toxicity. Larger or symptomatic lesions are of higher priority for SBRT. At least one target lesion will not receive SBRT, to evaluate ORR. The scatter radiation dose to this target lesion should be monitored if located less than 6cm from the irradiated lesions.

All subjects will be treated until progression of disease, unacceptable toxicity, or subject withdrawal of consent. Palliative radiation therapy will not be permitted while being treated under the protocol. The need for palliative radiation therapy will be considered progressive disease.

Study Population: Metastatic Merkel cell carcinoma subjects

Key Inclusion Criteria:

- At least 18 years of age
- ECOG PS < 2
- Active disease measurable by CT or MRI.
- Prior chemotherapy or immunotherapy will be allowed if new or persistent measurable site(s) of disease are present.
- Prior radiation therapy will be allowed if there is active measurable disease burden.

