1.2 Study Rationale

The proposed trial is a Phase 2 randomized, multi-institutional study of nivolumab and ipilimumab with or without SBRT in subjects with metastatic Merkel cell carcinoma. Merkel cell carcinoma (MCC) is a rare and aggressive cutaneous neuroendocrine malignancy with a propensity for distant metastasis with a 5 year survival rate of 25% in metastatic patients¹. Currently, there is no standard of care or no available treatment for this patient population. Mono- or polychemotherapy can be used in metastatic MCC, but responses are generally short-lived with poor outcome². Therefore, there is a significant need for improved therapeutic approach for metastatic MCC patients. Unfortunately, studies to define standard care have been limited by the rarity of this cancer.

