1.5.5 Summary of Clinical Activity

Nivolumab Monotherapy

Several immune checkpoint inhibitors targeting PD1 or PD-L1 are being tested currently. A recent interim report of phase I/II trial of metastatic treatment-naive MCC patients on pembrolizumab reported 14% complete response rate¹⁰. Therefore, we anticipate a significant therapeutic efficacy of

nivolumab in MCC, which is being evaluated in an on-going multi-institutional clinical trial on Nivolumab alone for virus-associated cancers including MCC conducted by BMS.

Otherwise, the clinical activity of nivolumab was demonstrated in multiple tumor types. In CA209003³⁸ the clinical activity of nivolumab was demonstrated in melanoma, RCC, and NSCLC. Clinical activity was noted across a range of doses (0.1 mg/kg, 0.3 mg/kg, 1 mg/kg, 3 mg/kg, 10 mg/kg). In CA209003, as of the clinical cut-off date of 03-Jul-2012, a total of 304 subjects with melanoma, RCC, and NSCLC have been evaluated for clinical activity. A response of either CR or PR, as determined by investigator assessed tumor evaluations based on modified RECIST 1.1, has been reported at all dose levels. No responses (CR or PR) have been reported in subjects with colorectal carcinoma or castrate-resistant prostate cancer.

Among 106 subjects with advanced melanoma who received nivolumab and were evaluable for response, the preliminary objective response rates were 6/17 (35%), 5/18 (28%), 11/34 (32%), 7/17 (41%), and 4/20 (20%) for melanoma subjects treated at 0.1, 0.3, 1, 3, and 10 mg/kg, respectively. Duration of response range from 3.6 to 11.2, 1.8 to 9.2, 1.9 to 24.9, 9.2 to 22.4, and 17.0 to 25.7 months in the melanoma subjects treated at 0.1, 0.3, 1, 3, and 10 mg/kg, respectively. Stable disease over 24 weeks occurred in an additional 1/18 (6%), 4/34 (12%), 1/17(6%) melanoma subjects at 0.3, 1, and 3 mg/kg, respectively. Finally, the PFS-24 week was 41%, 33%, 48%, 55%, and 30% in melanoma subjects treated at 0.1, 0.3, 1, 3, and 10 mg/kg, respectively.

SBRT Monotherapy

The local control rate of irradiated tumors following SBRT is excellent. For instance, five-year local control rate stage I non-small cell lung cancer patients treated with 54 Gy in 3 fractions is in excess of 80%⁹⁶. On a particular note, MCC metastases treated with SBRT to 8Gy in a single fraction achieved complete responses in 45% of tumors with durable local control in 77% of treated tumors with a median follow up of 277 days²⁴.

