6 RADIATION THERAPY

Metastatic lesions with the following distribution are eligible to be treated with SBRT on this protocol:

1 – 4 metastases distinct from the measurable target lesion that will not be irradiated to evaluate responses to the abscopal effect and immunotherapy. Larger lesions are given preference for SBRT to maximize tumor antigen release. The irradiated lesion will not be included in the calculations for measurable disease.

SBRT will be given Week 2 - 3, please see Section 5.5 and 6. SBRT should begin Week 2, and therefore, the radiation planning process should begin as the patient is registered for the study prior to randomization. SBRT for all metastases should be completed within 2 weeks of the first dose of SBRT. Not all metastases need to receive radiation therapy on the same day.

Most commercially available photon producing treatment units are allowed. As such, conventional linear accelerators, specialized linear accelerators with image guidance (e.g., Novalis, Trilogy, Synergy, Artiste, TrueBeam) are allowed. These units can be used with conformal dose delivery or IMRT. Specialized dose painting accelerators (e.g., Cyberknife, Gammaknife or Tomotherapy) are allowed provided they meet the technical specifications of the protocol and are used in a fashion that passes the credentialing required by the protocol. Conventional linear accelerators without add-on IGRT must have some other IGRT capability like CT-on-rails in the treatment room.

IGRT is required for this study. Either 3DCRT or IMRT (including VMAT) are all acceptable planning techniques. Planning techniques may differ for each lesion to be treated provided that the tumor motion is properly accounted for with each technique when the target or targets are in or near the thorax region.

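### Local control of irradiated lesions is planned as Kaplan-Meier with no rule for death and no stated unit; if deaths are censored, 24-month local failure is overstated by about 2 to 10 points, depending on assumptions

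*Combined protocol and SAP*

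**What the plan says.** Local control of irradiated tumor is a secondary objective (Section 1.3.2). Section 9.3.2.2 sets out the analysis: "The local control (LC) of irradiated lesions will be conducted using a two-sided log-rank test stratified by prior immunotherapy exposure at screening in randomized subjects". A Cox model with arm as the only covariate follows, and then: "LC medians with 95% CIs and LC rates at 12 and 24 months with 95% CIs will be estimated using Kaplan-Meier methodology".

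The number of irradiated lesions varies by patient. Section 6 allows "1 – 4 metastases distinct from the measurable target lesion that will not be irradiated". The synopsis leaves the number open: "The number of lesions receiving SBRT will be at the treating physician's discretion based on anticipated toxicity".

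The unit of analysis is not stated. Section 9.2.2 says the endpoint "will be assessed by the local control rate of the irradiated lesion", in the singular, while Section 9.3.2.2 speaks of lesions in the plural.

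Death is not addressed for this endpoint. Section 9.2.2 gives event and censoring rules for PFS and OS but none for local control. The local-control entry in Section 7.4.1 is a remark on tumor biology, with no event rule, time origin or handling of death. Neither a competing-risk method nor a clustered variance is mentioned for local control.

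**The concern.** Two features of this endpoint make plain Kaplan-Meier with ordinary intervals a poor default.

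First, some patients will die with their irradiated lesions still controlled. Treating those deaths as censoring estimates what would happen if nobody died. That figure is higher than the share of patients or lesions that actually fail locally.

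Second, lesions in one patient share host, tumor biology and treatment, so their outcomes are probably correlated. Counting them as independent overstates the information in at most about 24 Arm B patients (Section 9.1.1).

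At stake is the trial's direct readout of what SBRT does to the lesions it treats. It could be reported as worse than it was, and with more apparent precision than the data hold.

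The same paragraph's log-rank test and Cox model compare arms, although Arm A receives no SBRT. That is a separate matter. The point here remains when Arm B is described alone.

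**Working it through.** The documents give no expected rate, event count or power for local control, so there is no plan figure to reproduce. The sizes below use figures quoted elsewhere in the protocol, turned into hazards by assumption.

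**Inputs**
- Mortality (Section 1.2): metastatic disease "with a 5 year survival rate of 25% in metastatic patients".
- Local control in Merkel cell carcinoma after a single 8 Gy fraction (Section 1.5.5): "durable local control in 77% of treated tumors with a median follow up of 277 days".
- Local control in stage I lung cancer after 54 Gy in 3 fractions (Section 1.5.5): above 80% at five years. I use 80%.
- Irradiated lesions per patient (Section 6): 1 to 4, distribution not given.
- Arm B size (Section 9.1.1): 24 at full accrual.

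**Step 1: death as a competing event**

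Assume constant hazards, h for local failure and d for death without it, with t in years.
- Kaplan-Meier failure with deaths censored: 1 − exp(−ht).
- Cumulative incidence: h/(h+d) × [1 − exp(−(h+d)t)].

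Mortality: d = −ln(0.25)/5 = 0.277 per year, so 1 − exp(−0.277×2) = 42.6% are dead by 24 months.

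Three readings of local failure:
- A, 80% control at five years: h = −ln(0.80)/5 = 0.0446.
- B, 77% taken as the 24-month rate: h = −ln(0.77)/2 = 0.131.
- C, 77% taken as the probability at day 277 and extrapolated: h = −ln(0.77)/(277/365.25) = 0.345.

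Worked example for C at 24 months: 1 − exp(−0.689) = 49.8%, against 0.345/0.622 × [1 − exp(−1.244)] = 39.4%.

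| Reading | Time | 1 − KM | Cumulative incidence | Gap (points) |
|---|---|---|---|---|
| A | 12 mo | 4.4% | 3.8% | 0.5 |
| A | 24 mo | 8.5% | 6.6% | 2.0 |
| B | 12 mo | 12.3% | 10.7% | 1.5 |
| B | 24 mo | 23.0% | 17.9% | 5.1 |
| C | 12 mo | 29.2% | 25.7% | 3.5 |
| C | 24 mo | 49.8% | 39.4% | 10.4 |

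In-trial mortality is also unknown. Varying 24-month mortality from 8.5% to 75% moves the 24-month gap to 0.4–3.9 points (A), 1.0–10.2 (B) and 1.9–20.8 (C). At 23% Kaplan-Meier failure, a 10-point gap needs about 74% dead by 24 months. At 40% failure it needs about 49%. At 10% failure it cannot occur.

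**Step 2: lesions within patients**

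The design effect is 1 + (k−1)ρ, and the standard error grows by its square root. With k = 2.5 (the mean of 1 to 4), ρ = 0.2 gives √1.30 = 1.14 and ρ = 0.5 gives √1.75 = 1.32. The correlations are assumed.

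A simulation (4,000 runs, 24 patients, 1 to 4 lesions each with equal probability, shared gamma frailty, about 43% dead by 24 months) compared the true standard error with the lesion-level Greenwood value.

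| Kendall's tau | Ratio, 23% failure | 95% CI coverage | Ratio, 40% failure | 95% CI coverage |
|---|---|---|---|---|
| 0.20 | 1.11 | 93.6% | 1.15 | 91.7% |
| 0.67 | 1.41 | 86.1% | 1.45 | 83.9% |

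With independent lesions coverage was 95–96%. With one record per patient k = 1, the design effect is 1 and the problem disappears.

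**The case against.** The case against rests on what the plan leaves open.

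**The unit may be the patient.** Section 9.2.2 uses the singular, and Section 9.3.2.2 places the analysis in randomized subjects. On that reading clustering never arises. This stands: narrow intervals are a conditional risk, because the plan neither states nor excludes lesion-level records.

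**Censoring at death is not written down.** The PFS definition counts death as an event, and local control could follow it. There would then be no competing event, but the result would be survival free of local failure. Under reading C, exp(−0.622×2) = 28.8% would be alive and controlled at 24 months, so 71.2% would have an event, against 49.8% by censoring and 39.4% by cumulative incidence. This objection stands too, and the spread shows why the rule must be fixed in advance.

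**Kaplan-Meier can be a legitimate target.** It estimates tumor control with death removed, if censoring is independent. Under reading C, cumulative incidence leaves 60.6% without local failure, but 60.6 − 28.8 = 31.8 points of that have died. Neither number is simply the true one. This mostly stands. However, the plan states no such target, and independence is doubtful: the Section 7.1 tables run surveillance only up to distant recurrence, and Section 4.1 ends off-treatment surveillance at progression. Progression elsewhere may well be related to local failure.

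**The 10-point figure is the top of the range.** It treats a proportion reported with a median follow-up as a probability at that day, and extends it at constant hazard, although the source describes the control as durable. It also comes from a single 8 Gy fraction, not 24 Gy in 3 fractions with two checkpoint inhibitors. This stands.

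**Conclusion.** The point holds in conditional form. Section 9.3.2.2 commits to Kaplan-Meier for local control without a rule for death or a stated unit, in a setting with up to four irradiated lesions per patient and substantial background mortality.

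If deaths are censored, the direction is certain: one minus Kaplan-Meier exceeds the actual cumulative incidence. The size is about 2 to 10 points at 24 months if 25% five-year survival holds at constant hazard, and wider if mortality differs. If lesions are separate records, the true standard error is about 1.1 to 1.45 times Greenwood's under the assumed correlations.

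A reader might infer three stronger things. One is that local failure is overstated by 10 points outright; the documents give no in-trial local-failure or mortality rate, so that is one end of an assumed range. Another is that the intervals are too narrow as planned; that depends on a choice the plan does not make. The third is that the Arm B estimate is wrong in itself; it is defensible as net control under independent censoring.

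This is a cheap improvement. Local control is a secondary endpoint with no part in the Simon rule or the posterior comparison of response rates.

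**What to change.** In Section 9.3.2.2, for Arm B:
- Define the local-failure event, its time origin, and how lesions are followed or censored after progression elsewhere.
- Report the cumulative incidence of local failure at 12 and 24 months with death as a competing event. Show the incidence of death without local failure beside it, so that lesions in patients who died are not read as lasting control.
- State the unit: time to first local failure per patient, or lesion-level data with patient-clustered intervals (robust variance or bootstrap by patient).
- Keep the Kaplan-Meier curve, if wanted, as a supplementary estimate labelled as control with death censored. The median need not be dropped; if it is not reached, report that.

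The cost is SAP wording and a little more programming, with slightly wider intervals. It needs no additional patients.

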9.3.3 Safety Analyses

Safety analyses will be performed in all treated subjects. Descriptive statistics of safety will be presented using NCI CTCAE version 4.0 by treatment group. All on-study AEs, treatment-related AEs, SAEs, and treatment-related SAEs will be tabulated using worst grade per NCI CTCAE v 4.0 criteria by system organ class and preferred term. On-study lab parameters including hematology, chemistry, liver function, and renal function will be summarized using worst grade NCI CTCAE v 4.0 criteria.

